4.4 Study Drug Accountability and Compliance

Subjects will be instructed to return all used empty bottles and unused study drug at each visit.

The investigator or their appointed designee is responsible for ensuring that deliveries of study drug are correctly dispensed and recorded, that the product is handled and stored safely and properly, and that it is only being given to subjects in accordance with this protocol.

Sites will keep a current log of drug accountability recording:

- What drug supply was received from the sponsor
- What drug supply was dispensed to each subject
- What drug supply is current in inventory
- What drug supply was destroyed or returned to the sponsor for destruction

Note: Drug accountability is the responsibility of the investigator; a written account will be required for all discrepancies.

If the study drug supplies appear to be damaged/missing upon arrival at the investigational site, the sponsor should be contacted immediately.

the sponsor's designated monitor must verify all accountability records during periodic monitoring visits. Unused and used study drug must be stored on site until such accountability has taken place and authorization is received from the sponsor or sponsor's designee that the study drug may be returned or destroyed.

To stay in the study, subjects will be required to have taken at least 75% of their study treatment doses. A subject will be considered non-compliant if they have missed more than 25% of the required doses between visits. The minimum number of required doses per 7 days is detailed below:

- Week 1: 11/14 doses (22 capsules)
- Week 2: 11/14 doses (44 capsules)
- Week 3 to 4: 21/28 doses (105 capsules)

If compliance is less than 75% or greater than 125% at any visit, the reason(s) must be noted and the subject's continued participation in the study should be discussed with the study safety representative. Subjects should not make up for missed doses.

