4.5 Dose Adjustments / Toxicity Management

Adverse events will be graded for intensity by the investigator (see [Section 10.2.2.2](#)).

Dosing will be discontinued for all Grade 4 AEs.

In all subjects with intolerable AEs (as defined in [Section 10.2.1](#)) that are considered related to study drug, treatment should be suspended for up to 48 hours or until the AE resolves to a tolerable level of severity, whichever is earlier. Dosing may then be resumed at a previously tolerated lower dose (or 2 mg BID in the case of 4 mg BID). Only a single dose-step reduction (e.g. 10 mg BID to 8 mg BID, 8 mg BID to 4 mg BID, or 4 mg BID to 2 mg BID) is permitted. Re-up-titration is NOT permitted. Dosing should be discontinued if there is recurrence of intolerable AEs after dose reduction. Subjects on the 2 mg BID dose with intolerable AEs will be discontinued from treatment. Table 2 details dose reductions by dose level.

All subjects who discontinue treatment due to AEs will be followed for AE outcome. All AEs should be followed for resolution or for 30 days from the last dose of study drug, whichever is shorter.

Table 2: Study Drug Dose Reduction for Intolerable AEs

Dose and Schedule of Study Drug	Dose Reduction
2 mg BID	Remove from treatment ¹
4 mg BID	2 mg BID
8 mg BID	4 mg BID
10 mg BID	8 mg BID

1 – Subjects who are removed from treatment for AE(s) should be followed for resolution of the AE(s) and should complete all assessments scheduled for the EOS/FU Visit as well as all assessments that they are capable of completing on the Visit day if the decision to remove from treatment is made on a Visit day. Likewise, if the investigator plans to temporarily interrupt dosing because of an AE and the decision is made on a visit day, then the subject should complete all scheduled assessments that they are capable of completing on the visit day they appear.

The study safety representative should be notified of all dose reductions as soon as is feasible.

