6.4 Withdrawal of Subjects and/or Discontinuation of Treatment

A subject should be withdrawn from the study for any of the following:

- 1) Withdrawal of subject consent
- 2) Subject is lost to follow-up
- 3) Investigator determines that withdrawal from the study is in the best interest of the subject.
- 4) Subject is non-compliant with protocol-mandated activities.
- 5) Occurrence of any intercurrent condition, injury, or disease that becomes apparent during the study and necessitates the termination of the subject from the study.
- 6) Administrative reason (e.g., termination of the clinical study by a regulatory agency or the sponsor)

A subject should be discontinued from treatment for any of the following:

- 1) Subject is not at least 75% compliant with study drug administration at any study visit ([Section 4.4.](#))
- 2) Occurrence of defined unacceptable toxicity ([Section 4.5](#))
- 3) Investigator determines that discontinuation of treatment is in the best interest of the subject.
- 4) Occurrence of any intercurrent condition, injury, or disease that becomes apparent during the study and necessitates the discontinuation of treatment.
- 5) Pregnancy
- 6) Subject requires use of prohibited concurrent medication
- 7) Subjects answering "yes" to Suicidal Ideation item 4 or 5 on the C-SSRS during the study must be withdrawn from the study treatment. Investigators should also withdraw subjects from treatment if, in the judgment of the investigator, the subject develops other indicators of significant risk of suicide. In the event that suicidal ideation is observed in any study subject, the investigator will manage the situation as he/she deems medically and psychiatrically appropriate.

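### Minor rule conflict: 6.4 item 1 tells sites to stop treatment below 75% compliance while 4.4, 7.2.3 and 7.2.4 call for discussion, and none exempts doses withheld under 4.5 or adapts the capsule minima to a reduced dose

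*Protocol*

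**What the plan says.** The file holds several versions of the protocol. Section numbers here refer to the latest one, which plans about 106 subjects.

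- **4.4 (compliance).** Staying in the study requires at least 75% of doses. The definition is: "A subject will be considered non-compliant if they have missed more than 25% of the required doses between visits". Printed beneath it are minima of 11/14 doses (22 capsules) for Week 1, 11/14 (44 capsules) for Week 2 and 21/28 (105 capsules) for Weeks 3 to 4. Missed doses are not made up. The consequence is procedural. For a count under 75% (or over 125%) the site records why, and whether the subject carries on is a matter for consultation: "continued participation in the study should be discussed with the study safety representative".
- **4.5 (toxicity).** Where an intolerable adverse event is attributed to the drug, the instruction is: "treatment should be suspended for up to 48 hours or until the AE resolves to a tolerable level of severity, whichever is earlier". Afterwards the subject may restart one step lower, and "Re-up-titration is NOT permitted".
- **6.4 (discontinuation).** Item 1 in the list of reasons for stopping treatment reads: "Subject is not at least 75% compliant with study drug administration at any study visit". It cross-refers to 4.4.
- **7.2.3 and 7.2.4 (Visits 2 and 3).** If compliance is below 75%, up-titration is to be discussed with the study safety representative.
- **7.1, note 28.** Compliance is measured by pill count.

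**The concern.** Two things do not fit together.

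First, the consequence of falling below 75% differs by section. Item 1 of 6.4 lists it as a reason for stopping treatment, with no qualifier of its own. Sections 4.4, 7.2.3 and 7.2.4 treat it as a matter for discussion, and the two visit sections contemplate even a dose increase. The text does not say whether item 1 applies before or after that discussion.

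Second, the compliance count takes no account of what 4.5 instructs. Withheld doses are not removed from the fixed denominators, and the capsule figures assume the full scheduled dose. A subject who followed every instruction can therefore be scored as non-compliant.

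The subjects concerned have a drug-related intolerable event and are ones whom 4.5 means to allow to continue. Discontinued subjects are not replaced (6.4.2) and the primary endpoint is at Day 28 (3.3.1), so any needless discontinuation before Visit 4 costs on-treatment primary data.

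**Working it through.** **Inputs.** Dosing is twice daily, every 12 ± 2 hours (7.2.2). Capsules per dose are 2, 4 and 5 in Week 1, Week 2 and Weeks 3–4 (4.3). Maximum suspension is 48 h (4.5). The threshold is 75% (4.4). Visits 2 and 3 have a window of ± 2 days (Table 3).

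**The printed minima reproduce.** Doses: 0.75 × 14 = 10.5, rounded up to 11; 0.75 × 28 = 21. Capsules: 11 × 2 = 22, 11 × 4 = 44, 21 × 5 = 105. The capsule figures are therefore the dose minima converted at the unreduced 4, 8 and 10 mg doses.

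**Suspension.** 48 h / 12 h = 4 doses withheld. If every other dose is taken over an interval of d days, compliance is (2d − 4)/(2d):

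| Days between visits | Doses taken / scheduled | Compliance | Against 75% |
|---|---|---|---|
| 5 | 6/10 | 60.0% | fails |
| 6 | 8/12 | 66.7% | fails |
| 7 (nominal) | 10/14 | 71.4% | fails |
| 8 | 12/16 | 75.0% | passes |
| 9 | 14/18 | 77.8% | passes |

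Three withheld doses at 7 days give 11/14 = 78.6%, which passes. In Weeks 3–4 a full suspension gives 24/28 = 85.7%, which also passes.

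**How narrow the 7-day case is.** If suspension starts s hours after the last dose (0 < s < 12), the fourth dose falls due 48 − s hours into it. It is lost only if the event resolves after that point and by 48 h, a window of at most 12 h. If the 48 h is counted from the last dose to the next, only three doses are lost. An event that has not settled to Grade 1 or Baseline by 48 h ends treatment under 4.3.1 in any case.

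**Capsules, with every prescribed dose taken.** Let x be the number of doses taken before the reduction.

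- Reduced to 2 mg BID in Week 1, then all of Week 2 at that dose (no re-up-titration): 14 × 1 = 14 capsules against 44 at Visit 3, with 14/14 doses.
- Reduced 4 to 2 mg within Week 1: 2x + (14 − x) = 14 + x, below 22 when x ≤ 7 (21 at x = 7).
- Reduced 8 to 4 mg within Week 2: 4x + 2(14 − x) = 28 + 2x, below 44 when x ≤ 7 (42 at x = 7).
- Reduced to 4 mg BID in Week 2, then Weeks 3–4 at that dose: 28 × 2 = 56 against 105, with 28/28 doses. No visit falls between Visits 3 and 4, so this is first seen at Visit 4, when dosing ends.
- Reduced 10 to 8 mg with nothing withheld: 5x + 4(28 − x) = 112 + x, never below 105.

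**The case against.** The best defence is that the protocol already routes these subjects to a person. Item 1 of 6.4 says should and points to 4.4, where the reason is recorded and the case discussed. Sections 7.2.3 and 7.2.4 expect subjects below 75% to reach Visits 2 and 3 with dosing still open. The study safety representative must also be told of every dose reduction (4.5), so the reason for a shortfall will usually be known. This largely stands. A reader might infer that such subjects are removed automatically, and the documents do not support that. What remains is that item 1, followed as written, points the other way and no order of precedence is given.

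It can also be said that a dose the investigator withholds is neither required nor missed. That is a sensible reading, but 4.4 does not state it and prints fixed denominators of 14 and 28.

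On capsules, the operative criterion is the number of doses, and the bracketed figures are conversions. A reader might infer a separate capsule test that dose-reduced subjects fail. The text sets no such test, and these subjects can still meet the dose minimum. The residual fault is that compliance is measured by pill count while the only printed capsule figures are wrong for a reduced dose.

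Finally, efficacy is analysed in all randomized subjects (11.4), so a non-compliance label does not itself exclude anyone from that population. No error rate or power figure changes.

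**Conclusion.** A real but minor conflict between rules. On a nominal 7-day interval in Week 1 or 2, a full 48-hour suspension leaves 71.4% against a required 11/14, so a protocol-adherent subject whom 4.5 allows to resume literally meets a listed reason for discontinuation. This assumes that four doses are withheld, all others are taken, and required doses means the printed denominators. It will be rare.

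The capsule case that matters is the subject reduced to 2 mg BID in Week 1, with 14 capsules against 44 at Visit 3. The shortfall in Weeks 3–4 has little consequence because it appears only at the end-of-dosing visit.

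The likely effect is uneven handling of a few subjects. The protocol gives no rate for suspensions or reductions, so no number affected can be stated.

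**What to change.** In 4.4, state that doses withheld under 4.5 are not required doses, and that the capsule minima are counted at the dose actually prescribed. The suspension example then becomes 10/10 = 100%. The Week 2 minimum for a subject on 2 mg BID becomes 11 × 1 = 11 capsules, which 14 satisfies.

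In 6.4 item 1, state that the 75% criterion uses the 4.4 definition and is applied after the discussion described there.

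The cost is one or two sentences in 4.4 and one clause in 6.4. The practical burden is that suspension and reduction dates must be used when compliance is calculated. Sample size, design and analysis are unchanged.

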4.5 Dose Adjustments / Toxicity Management

Adverse events will be graded for intensity by the investigator (see [Section 10.2.2.2](#)).

Dosing will be discontinued for all Grade 4 AEs.

In all subjects with intolerable AEs (as defined in [Section 10.2.1](#)) that are considered related to study drug, treatment should be suspended for up to 48 hours or until the AE resolves to a tolerable level of severity, whichever is earlier. Dosing may then be resumed at a previously tolerated lower dose (or 2 mg BID in the case of 4 mg BID). Only a single dose-step reduction (e.g. 10 mg BID to 8 mg BID, 8 mg BID to 4 mg BID, or 4 mg BID to 2 mg BID) is permitted. Re-up-titration is NOT permitted. Dosing should be discontinued if there is recurrence of intolerable AEs after dose reduction. Subjects on the 2 mg BID dose with intolerable AEs will be discontinued from treatment. Table 2 details dose reductions by dose level.

All subjects who discontinue treatment due to AEs will be followed for AE outcome. All AEs should be followed for resolution or for 30 days from the last dose of study drug, whichever is shorter.

Table 2: Study Drug Dose Reduction for Intolerable AEs

Dose and Schedule of Study Drug	Dose Reduction
2 mg BID	Remove from treatment ¹
4 mg BID	2 mg BID
8 mg BID	4 mg BID
10 mg BID	8 mg BID

1 – Subjects who are removed from treatment for AE(s) should be followed for resolution of the AE(s) and should complete all assessments scheduled for the EOS/FU Visit as well as all assessments that they are capable of completing on the Visit day if the decision to remove from treatment is made on a Visit day. Likewise, if the investigator plans to temporarily interrupt dosing because of an AE and the decision is made on a visit day, then the subject should complete all scheduled assessments that they are capable of completing on the visit day they appear.

The study safety representative should be notified of all dose reductions as soon as is feasible.

4.6 Overdose Management

To date, no overdoses of CX-8998 in humans have occurred.

Because no humans have overdosed with CX-8998, specific information regarding treatment of overdose is not currently available. In case of an acute overdose, it is recommended that the stomach be emptied and oral gavage with activated charcoal be used to help reduce absorption of CX-8998. In the event of an overdose, the study safety representative should be contacted immediately.

4.7 Randomization and Matching of Subjects

Eligible subjects will be randomized in a 1:1 ratio between CX-8998 and placebo, using an Interactive Web Response System (IWRS). Subject randomization will be stratified by concomitant use of an anti-tremor medication and site type (substudy vs. non-substudy). A statistician not involved in the day-to-day study operation will create the randomization schedule. Details of the randomization process will be included in the study Operations Manual.

4.8 Study Blinding

This is a double-blind study; that is, the treatment assignment and drug contents are not revealed to the sponsor, the subject and or investigator and other study personnel.

Maintenance of the double-blind is critical to the integrity of this clinical study. However, in the event of a medical emergency or pregnancy (including pregnancy in the sexual partner of a male subject) in which knowledge of the investigational product is critical to the subject's management, the blind for that subject may be broken by the treating investigator.

Before breaking the blind for an individual subject, the investigator should have determined that the information is necessary, i.e., it will alter the immediate management of the subject's care. *In the majority of cases not involving pregnancy, because there is no known specific antidote for any potential pharmacodynamic or toxic effect of CX-8998, there should rarely be a need to unblind a subject to guide immediate medical management of an emergency.*

The need to break the blind should first be discussed with the sponsor's study safety representative, if at all possible. In case of an emergency, the investigator may use the Emergency Unblinding Function under the Randomization side menu in the IWRS. Once the decision to unblind has been made, the investigator must record the nature of the emergency that required the unblinding, along with the date and time of the unblinding, in the proper source documentation and notify the sponsor's study safety representative of the unblinding. However, the sponsor's study safety representative, and any other investigators, must not be informed of the treatment assignment. The treatment assignment must not be noted in the source documentation or any other documentation submitted to the sponsor.

Study treatment for a given subject may be unblinded for reportable safety events (e.g., suspected unexpected serious adverse reaction [SUSAR]) as required by local or other regulations, but the mere occurrence of an SAE should not routinely precipitate immediate unblinding.

In cases of accidental unblinding, the investigator will notify the sponsor's study safety representative and ensure that every attempt to preserve the blind is made. Specifically, the

investigator will not reveal the identity of the study treatment to the sponsor's study safety representative or other sponsor staff, any contract research organization (CRO) staff, including the clinical site staff, clinical research associate (CRA), subject, or anyone else who does not already know this information.

If unblinding occurs, the study drug must be discontinued for the particular subject(s) involved.

5 INVESTIGATORS, SITES AND DURATION

5.1 Investigators and Sites

The study will be conducted at multiple sites in the United States.

5.2 Central Reviewers

A central reviewer will review eligibility criteria for all subjects. The site will submit an eligibility checklist for evaluation of each subject. A central reader will score the screening TETRAS performance video to determine if the subject meets Inclusion Criteria 5 and 6 below. No subject may be enrolled, randomized or dosed with study drug prior to receipt of notification that the central reviewer and review process has deemed the subject eligible.

5.3 Duration of Study

Subjects will participate for a total of up to 12 weeks, including screening, the 4-week treatment period and follow-up.

5.4 Termination of Study

This study may be terminated at the discretion of the sponsor or the Food and Drug Administration (FDA) or in accordance with the recommendations set forth in the Safety Monitoring Plan ([Section 10.4](#)).

6 STUDY POPULATION

6.1 Number of Subjects

Approximately 106 eligible subjects will be randomized to treatment.

6.2 Inclusion Criteria

Subjects may be included in the study only if they meet all of the following criteria. Subjects may undergo rescreening following consultation with and approval of the study safety representative.

- 1) Signed informed consent form (ICF) indicating that the subject has been informed of the procedures to be followed, the experimental nature of the therapy, alternatives, potential benefits, side effects, risks, and discomforts.
- 2) Men or non-pregnant, non-breastfeeding women 18 to 75 years-of-age who are able to read and understand English.

- 3) Diagnosis of definite or probable bilateral essential tremor (ET) as defined by the Tremor Investigational Group with involvement of the hands and arms without present causes of enhanced physiologic tremor ([Deuschl et al., 1998](#)).
- 4) Diagnosis of ET before the age of 65
- 5) Tremor severity score of at least 2 in at least one upper extremity on at least one of the three maneuvers on the TETRAS scale.
- 6) Total TETRAS performance score of at least 15 (Note: Inclusion thresholds, including thresholds for criteria 5 & 6 shall NOT be shared with study subjects or caregivers to limit Baseline inflation.)
- 7) One concomitant anti-tremor medication (other than primidone) is allowed. Subjects must have been on a stable dose for at least one month prior to screening and must have no change in dose in the single concurrent anti-tremor medication for the duration of the study. Note that primidone is NOT an allowed anti-tremor medication. If on primidone, subjects are allowed to extend their screening period by 2 weeks (for a total of 6 weeks) and discontinue primidone under the supervision of the investigator.
- 8) Able and willing to comply with scheduled visits, treatment plan, laboratory tests, and other study procedures
- 9) Subjects with reproductive capability including all males and women of childbearing potential (WOCBP) must agree to practice continuous abstinence or adequate contraception methods (appropriate double barrier method or oral, patch, implant, or injectable contraception) from as soon as feasible during screening period until at least 30 days after the last dose (i.e., intermittent abstinence based on "rhythm", temperature monitoring, or other means of timing is not acceptable). WOCBP include any woman who has experienced menarche and who has not undergone successful surgical sterilization (hysterectomy, bilateral tubal ligation, and/or bilateral oophorectomy) or is not post-menopausal. Post-menopausal is defined as:
 - a) Amenorrhea \geq 12 consecutive months without another cause, and a documented serum follicle stimulating hormone (FSH) level > 35 mIU/mL;
 - b) Amenorrhea \geq 12 consecutive months in women ≥ 62 years old (FSH testing is not required).

Male subjects with a partner of childbearing potential must be surgically sterilized or be willing to use condoms with spermicide from as soon as feasible during screening period until at least 30 days after the last dose.

10. Approval by the sponsor medical personnel as to final suitability for the study

6.3 Exclusion Criteria

Subjects will be excluded from the study if any of the following conditions apply. Subjects may undergo rescreening following consultation with and approval of the study safety representative.

- 1) Exposure to tremorgenic drugs or drug withdrawal states within the 30 days prior to the first planned dose of study drug

- 2) Direct or indirect trauma to the nervous system within 3 months preceding the onset of tremor
- 3) History or clinical evidence of psychogenic tremor origin
- 4) Known history of other medical conditions that may cause or explain subject's tremor, including, but not limited to:
 - a) Parkinson's disease
 - b) dystonia
 - c) cerebellar disease, other than essential tremor
 - d) Traumatic Brain Injury
 - e) alcohol abuse or withdrawal
 - f) mercury poisoning
 - g) hyperthyroidism
 - h) pheochromocytoma
 - i) head trauma or cerebrovascular disease within 3 months prior to the onset of essential tremor
 - j) multiple sclerosis
 - k) polyneuropathy
 - l) family history of Fragile X syndrome
- 5) Prior MR-guided Focused Ultrasound or surgical intervention (e.g., deep brain stimulation, ablative thalamotomy or gamma knife thalamotomy) for treatment of tremor
- 6) Botulinum toxin injection in the 6 months prior to screening
- 7) Currently using more than one anti-tremor medication
- 8) Experiencing clinical benefit from and/or is not willing to discontinue primidone
- 9) Use of medication(s) (in the past month) that might produce tremor or interfere with the evaluation of tremor, such as but not limited to: CNS-stimulants, lithium, amiodarone, metoclopramide, theophylline, and valproate
- 10) Inability to refrain from use of medication/substance(s) that might produce tremor or interfere with the evaluation of tremor on study visit days, such as but not limited to stimulant decongestants, beta-agonist bronchodilators, caffeine, alcohol and tobacco, based on investigator assessment at baseline
- 11) Positive urine drug screen (phencyclidine (PCP), cocaine, cannabinoids, opiates/barbiturates, benzodiazepines, amphetamines, methadone or MDMA (ecstasy)) unless explained by use of an allowed prescription medication ([Section 10.1.6](#)).
- 12) Regular use of more than two units of alcohol per day. See [Section 7.3.2](#) for definitions.

- 13) Sporadic use of a benzodiazepine, sleep medication or anxiolytic to improve sleep performance. Stable use at a consistent dose is allowed as long as tremor persists against the background of regular medication use. Use on the evening prior to a study visit is prohibited.
- 14) Use of prescription or non-prescription drugs or other products (i.e. grapefruit juice) known to be strong inhibitors or inducers of CYP3A4 which cannot be discontinued 2 weeks prior to Day 1 of dosing and withheld throughout the study, including primidone
- 15) Concurrent illnesses that would be a contraindication to trial participation, including, but not limited to:
 - a) Severe arterial thromboembolic events (myocardial infarction, unstable angina pectoris, stroke) less than 6 months before screening
 - b) NYHA Class III or IV congestive heart failure, ventricular arrhythmias or uncontrolled blood pressure
 - c) Clinically significant ECG abnormality per the investigator assessment or any of the following:
 - i) QTcF >450 msec (males) or >470 msec (females)
 - ii) PR interval >250 msec
 - iii) Atrioventricular block of second degree or higher, including Mobitz I
 - iv) Persistent sinus bradycardia < 50 beats per minute; persistent means the bradycardia is present on the first ECG and on one repeat ECG performed on another day
 - v) For other ECG findings (e.g., including, but not necessarily limited to, tachycardia, bundle branch block, frequent ectopic beats, etc.) the investigator should send a scanned, identity-blinded copy of the ECG tracing to the study safety representative for review
 - vi) The presence of a cardiac pacemaker does not automatically exclude eligibility. The specifics must be discussed with the study safety representative to make a determination of eligibility.
 - d) Known infection with HIV, hepatitis B, or hepatitis C, unless curative therapy completed for hepatitis C with negative PCR
 - e) Significant hepatic (AST/ALT > 2X upper limit of normal) or renal disease (creatinine clearance <39 mL/min)
 - f) Significant psychiatric history including mood disorders and alcohol or substance abuse within the last year
 - g) A current C-SSRS score of 4 or 5 at screening, or history of suicide attempt at any time during the past year
 - h) Clinically significant impaired balance or is considered at increased risk for falls
 - i) Symptomatic orthostatic hypotension

- 16) Psychological, social, familial, or geographical reasons that would hinder or prevent compliance with the requirements of the protocol or compromise the informed consent process
- 17) Any other condition and/or situation that causes the investigator to deem a subject unsuitable for the study (e.g., due to expected study medication non-compliance, inability to medically tolerate the study procedures, or a subject's unwillingness to comply with study-related procedures)
- 18) Treatment with an investigational agent within 30 days prior to the first dose of CX-8998 or planning to receive an investigational agent during the study

